5.2 Anticipated adverse device effects

There is no expected side effect in using Healsea® Babykids nor the Placebo.

No adverse effect is expected with the Placebo.

5.3 Risk associated with the participation in the clinical investigation

The assessments planned in the clinical investigation are questionnaires with no associated risk.

5.4 Possible interaction with concomitant treatments as considered under the risk analysis

No interaction is expected. Nevertheless, parents/legal guardians will be instructed to respect a 60-minute minimum interval after administration of the investigational medical device before administration of another local medication e.g., decongestant or mucolytics (if permitted) on their child.

5.5 Steps that will be taken to control and mitigate the risks

5.5.1 Healsea® Babykids

In line with NF EN ISO 14971:2019 standard (Medical Devices - Application of risk management to medical devices), a risk analysis has been conducted to estimate the risks associated with each step of the device lifecycle. Most of the risk has been mitigated through product design and manufacturing. The residual risk to patients who are administered this intervention is low. A list of potential risks associated with the device, procedures undertaken to minimise them, and methods used for their management is described in the device Risk Management Process File.

Considering:

- the risk analysis (ISO 14 971 activities) that demonstrates:
 - There is no longer High-level risk,
 - That, the 12 Medium risk level residual risks have an acceptable benefit-risk balance,
 - And all the others residual risks (62) are at Low risk.
 - Healsea® Babykids can be considered as safe and effective

and regarding the evaluation of benefit/risk profile, as detailed in the Clinical evaluation report, considering:

- The clinical data of the equivalent device (Physiomer® Spray Hygiène du nez)
- The currently available data on products use for the treatment of nasal cold and flu symptoms and the prevention of upper respiratory tract infections

it can be concluded that the benefit/risk ratio of Healsea® Babykids is acceptable, in compliance with essential requirements.

5.5.2 Placebo

Isotonic saline nasal solutions are well known for cleansing and hydrating the nasal mucosa without any safety concern. No risk analysis has been conducted to estimate the risk associated with each step of this device lifecycle. Anyway, the residual risk for the Placebo is expected to be lower than for Healsea® Babykids since this latter contains Symbiofilm® and isotonic saline solution and therefore represents the worst case. Thus, the Placebo used during this study can also be considered as safe.

5.5.3 Mitigation of risk during the clinical investigation

Although no obvious specific risk is identified for subjects participating in the study, and according to the requirements of ISO 14155:2020, some specific points have been identified requiring particular attention to guarantee the safety and the well-being of the subject.

As the study will be conducted in a blinded manner in minors, stringent risk acceptability thresholds per site are defined in the Study Risk Management Plan. Because of the paediatric population of the study, any issue with the informed consent process, any major protocol deviation or any serious incident are deemed unacceptable and shall trigger an immediate action plan.

Page **27** of **64** Version 1.1 –2023.02.02

More generally, the number of unreported incident/serious incident or adverse event per site, the timelines for materiovigilance/vigilance reporting to sponsor, the dispensation issues (number of devices delivered different from the number reported in the e-CRF), inadequate process to ensure the traceability of the investigational product, number of patient diary not collected at V2 shall be tracked according to the risk management plan in which risk acceptability thresholds are defined.

All issues shall be tracked according to the risk management plan and shall trigger an immediate action plan if the threshold is reached.

Should a potential unanticipated risk be detected, an action plan will be implemented with no delay.

5.6 Rational for the benefit risk ratio

Although infectious rhinitis is in most cases self-limiting, it impacts the children's quality of life during generally about 7 to 10 days. Furthermore, bacterial over-infections with worsening of symptoms can occur requiring antibiotic prescription. Progression to a chronic state, i.e. chronic rhinosinusitis is also observed.

Conventional therapies for infectious rhinitis are symptomatic and are not without side effect. For example, decongestant use can increase blood pressure, antihistamine intake is associated with drowsiness.

Healsea® Babykids represents an interesting alternative because this nasal spray could alleviate infectious rhinitis symptoms but also limit the complication and progression to chronic state.

Furthermore, there is no expected side effect.

6. Objectives and hypotheses of the clinical investigation

6.1 Hypothesis

Our hypothesis is that Healsea® Babykids nasal spray can improve the symptomatology of acute rhinitis with more efficacy than an isotonic saline nasal spray used as Placebo.

6.2 Primary Objective

To assess the efficacy of Healsea® Babykids on the overall health status score of the Acute Rhinitis Symptoms Severity Questionnaire (ARSSQ) in 2-6 years old children during a treatment period of 7 to 10 days as compared to Placebo.

6.3 Secondary Objectives

- To assess the impact of **Healsea® Babykids** on the duration of each infectious rhinitis symptom and on quality of life as compared to Placebo.
- To assess the impact of **Healsea® Babykids** on the intake of conventional common cold medication (antibiotics, antipyretics, mucolytics, decongestants, antitussives, systemic and topical corticosteroids) as compared to Placebo.
- Safety: to assess systemic and local tolerance of **Healsea® Babykids** over the study period.

6.4 Scientific justification and clinical relevance for effect sizes, noninferiority margins or equivalence

This is a PMCF study. The primary endpoint is a customized symptom and quality of life questionnaire. An arbitrary cohort of 200 children has been chosen. A cohort of 100 children in the Healsea® Babykids arm and 100 children in the Placebo arm is anticipated to allow to demonstrate the interest of using Healsea® Babykids in the acute infectious rhinitis. Indeed, 100 patients by arm are enough to detect a Cohen's effect size of 0.4 with a power of 80% and a type I error of 5%. Cohen's effect size is defined as the standardized difference between AUC in groups. According to Cohen's methodology, 0.4 is an intermediate size between a small effect (0.2) and a medium effect (0.5) and is coherent with the expected result. The Placebo arm will be used as the reference group.

The recruitment will be performed using a 1:1 randomization ratio.

6.5 Risks and anticipated adverse effects that are to be assessed

No specific risk for subject participating in the study is identified, provided that the eligibility criteria are fulfilled. The safety and well-being of subjects will be monitored throughout the study and a Risk Management Plan has defined stringent risk acceptability thresholds (see 5.5.3).

Version 1.1 –2023.02.02 Page **29** of **64**

7. Design of the clinical investigation

7.1 General

7.1.1 Design type of clinical investigation

This is a two-arm, double-blind, parallel group, randomized controlled trial (RCT).

The primary endpoint ARSSQ will be assessed once daily. After D8, the ARSSQ will be assessed once daily until the subject feels not sick for two consecutive days.

7.1.2 Measures to be taken to minimize or avoid bias

Randomization:

The random product attribution will be performed after checking that the eligibility criteria are fulfilled, thus minimizing the selection bias. Each site will receive several treatment blocks in accordance with the randomization table generated by Axiodis (blocks of 4). During the V1 visit, the investigator will deliver a product (active or placebo) to the patient in chronological order using the list of treatments allocated to the respective site. This method allows to maintain the 1:1 balance in a multicentric study.

Example: the site 01 received 3 treatment blocks, i.e. 12 treatments, number 001 to 012. For the patient 01-001, the investigator will deliver the treatment 001. The site 02 received 3 treatments blocks, i.e 12 treatments, number 013 to 025. For the patient 02-001, the investigator will deliver the treatment 013.

Blinding and unblinding:

The randomization list will be drawn up using a validated software and before the beginning of the study, by a statistician (at Axiodis) not involved in the study. The master randomization list will be stored confidentially until the study blind is broken at the end of study.

The randomization list will be:

- Transmitted by the Axiodis statistician to the person in charge of the product preparation,
 Creapharm
- Uploaded into the patient unblinding module of the eCRF

During the whole study and in the absence of unblinding, neither the investigators nor the subjects nor the staff involved (CRO, sponsor...) will be aware whether the product is Healsea® Babykids or the Placebo. Every effort will be made to maintain the blind during the study as well as during the follow-up period.

Both Medical Devices (Healsea® Babykids and Placebo) will be indistinguishable: same aspect, same packaging and same labelling of the vials.

The unblinding will occur after the database locking, at the end of the study. The statistician responsible for the randomization list will be in charge of the unblinding.

Emergency Unblinding:

In case of a medical emergency where knowledge of the blinded treatment is necessary for the treatment of an adverse event/incident, the investigator shall perform the unblinding via the unblinding module of the eCRF. The investigator shall send an e-mail informing about the unblinding with patient ID, date and reason of unblinding (the name of patient not to be communicated for GDPR compliance) to:

- The CRO in charge of the study coordination: [contact]
- The sponsor ([contact] and [contact] (vigilance manager))
- The statistician if charge of the randomisation list

The date and the reason for the unblinding will be indicated in the e-CRF and in the source document of the study.

7.1.3 Primary Endpoint with methods and timing for assessing recording and analysing variables

The AUC of the global score of the Acute Rhinitis Symptoms Severity Questionnaire (ARSSQ) during first 11 days of symptoms will be compared between both groups.

ARSSQ is a non-validated customized questionnaire (Appendice 1). It includes 10 items assessing symptoms, functional impairments, and global severity. Each item is scored from 0 (not present/no impact/ not sick) to 3 (severe, severe impact and very sick) for symptoms, functional impairment and global severity respectively. Parents/legal guardians will respond to questions according to the evolution of their child's symptoms. This questionnaire is based on the most common symptoms reported for children with common cold and on functional impairments easily evaluable by parents. In order to evaluate the time dependent efficacy of active/placebo, an AUC computation will be carried out.

The ARSSQ assessment will be completed in a paper diary once daily in the evening, taking into account the symptoms from the morning to the evening, within D2-D8 period. After D8, the ARSSQ will be assessed once daily until resolution of all symptoms for 2 consecutive days (question 1 of the questionnaire "not sick" ticked). At D1, the ARSSQ will be completed during the screening/inclusion visit V1. If the patient still has symptoms at V2, ("not sick" not ticked for 2 consecutive days in the previous days), the questionnaire will be also completed during the visit.

To be noticed that the duration may be censored at the end of study participation (visit V2, between day 15 and D18 after inclusion).

- 7.1.4 Secondary Endpoints with methods and timing for assessing, recording and analysing variables
- Comparison of duration of each cold symptom (questions 2 to 7 of the ARSSQ) in both groups.

For each separate symptom, the duration is defined as the number of days between Day 1 and the first day the parent/legal guardian reports the patient not having this symptom ("Not present") for 2 consecutive days.

As mentioned for primary endpoint, duration may be censored at Visit 2.

- Comparison of duration of quality-of-life impairment (questions 8 to 10 of the ARSSQ).

For each separate activity, the duration is defined as the number of days between Day 1 and the first day the parent/legal guardian reports no impact on the patient quality of life ("No impact") for 2 consecutive days.

As mentioned for primary endpoint, duration may be censored at Visit 2.

- Comparison of the frequency and number of days of concomitant treatments use that may affect common cold symptoms (antibiotics, antipyretics, systemic or local mucolytics, decongestants, antitussives, systemic and topical corticosteroids).

By reducing duration of the common cold symptoms, Healsea® Babykids will very likely reduce the use of common rescue medication. Concomitant treatments use will be reported in the paper diary by parents/legal guardians throughout the study, validated by the investigator at the end of the study visit before being reported in the e-CRF.

- **Safety:** Assessment of adverse event related to acute rhinitis and incidents throughout the study in both groups.

Adverse events/incidents will be reported in the paper diary by the parent , validated by the investigator at the end of study visit before being reported in the e-CRF.

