The investigator will provide the parents/legal guardians with the device according to the site specific treatment list, in order to respect the 1:1 randomization (blocks of 4). The investigator will explain how to use it.

NB: The first use of the device will be performed in the evening of the Day 1.

D1-D8 up to -D11 (at home):

The Parent/legal guardian will be asked to complete the ARSSQ in the diary, once daily in the evening. The symptoms occurring from the morning to the evening should be taken into consideration. The ARSSQ shall be scored at least from D1 to D8. Adverse events/incidents and concomitant medications are to be reported during the whole period

Between D8 and D11 (at home):

End of Healsea® Babykids/Placebo nasal spray.

➤ NB: The last study nasal spray intake will be performed **between D8 and D11** in the morning. The patient should stop taking the investigational device before D11 only if the question 1 "not sick" of the ARSSQ is ticked YES for 2 consecutive days.

Up to D15/D18 (at home):

Parents/legal guardians will continue to complete the paper diary daily (incidents/adverse events/expected undesirable sides effects, concomitant medications). For patients for whom common cold symptoms persist, parents/ legal guardians will be instructed to continue to complete the ARSSQ, until the subject feels not sick for two consecutive days.

Visit 2 (V2) - (Day 15-Day 18): end of study

The investigator or his/her delegated designee will:

- Perform a physical and clinical examination.
- Collect the patient diary.
- Review the paper diary to validate adverse events pertinent in the context of the common cold, incidents linked to medical device use and concomitant medications reported by the parents/legal guardians. Complete the e-CRF accordingly and report any new relevant safety events
- Ask parents/legal guardians to complete the ARSSQ if the patient still has symptoms.
- Assess the compliance to the treatment by weighing the device bottle returned by the parents/legal guardians. If a nasal spray is not returned or lost, the investigator will ask the

Version 1.1 –2023.02.02 Page **37** of **64**

Study Number: LPH-2202

parents/legal guardians to specify the number of missed nasal spray uses and will report the data into the e-CRF.

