6.4.7. AUC on global score of ARSSQ

The computation of the AUC on global score of the questionnaire will be made for patients with non-missing value at D1 and at least another non-missing time point between D2 and D11. Otherwise, the AUC will be missing.

The AUC will be computed by the trapezoidal rule from D1 to D11 (Acute Phase).

If the value at D11 is missing, then it will be estimated by the value at the last non-missing time point before D11.

AXIODIS CRO 13/47

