12. CHANGES IN THE CONDUCT OF THE STUDY OR PLANNED ANALYSIS

The planned analysis in the protocol to assess the primary objective (multivariate ANCOVA model of the AUC on global score of ARSSQ during the first eleven days of the study) has been replaced by the comparison of the means of the AUC on global score of ARSSQ during the first eleven days of the study between treatment groups. The multivariate ANCOVA has been put among secondary analyses.

This change has no impact on the relevance of the sample size calculation since the primary endpoint is the same as planned in the protocol.

Moreover, since several patients still reported having symptoms while they reported they did not feel sick anymore at the question 1 during at least the two last days of completion of the ARSSQ, their positive answers to the cold symptoms' items have been considered as non-significant. Consequently, the question 1 has been taken into account in addition to the corresponding items to determine the end of the cold symptoms' duration, however only on the condition that the last days of completion were consecutive.

If the last days of completion were not consecutive, positive answers to cold symptoms' items are still considered as symptomatic, even if the two last answers to the question 1 are negative. The symptom ends at the last symptomatic day if the patient reported the absence of this symptom at least twice and consecutively after this day. Otherwise, the duration of the symptom is censored at D18 or at the end of the study, whichever occurs first.

The same change has been applied to compute the duration of impact on QoL.

AXIODIS CRO 25/47

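### The daily ARSSQ can stop from D8 on Q1 alone while the primary AUC runs to D11, so up to 25% of the AUC weight is carried forward by design

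*Protocol*

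**What the plan says.** **Collection.** Protocol 7.4.1 sets the minimum: "The ARSSQ shall be scored at least from D1 to D8". For the days that follow, 7.1.3 states: "After D8, the ARSSQ will be assessed once daily until resolution of all symptoms for 2 consecutive days". The bracket after those words defines this as Q1 ticked 'not sick'. Section 7.4.1 gives children with persisting symptoms the same end point: "until the subject feels not sick for two consecutive days". The synopsis, 7.1.1 and the flow-chart footnotes in both documents agree. At V2 the ARSSQ is repeated only if the Q1 criterion has not been met (7.1.3, synopsis, SAP 3).

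**Primary endpoint.** The global score is the sum of ten items, each 0 to 3 (SAP 10.1). SAP 6.4.7 states: "The AUC will be computed by the trapezoidal rule from D1 to D11 (Acute Phase". A missing D11 value takes the last earlier value. Protocol 8.9 likewise specifies LOCF for children who stop before D11.

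**Durations.** Under Protocol 7.1.4 a symptom ends on "the first day the parent/legal guardian reports the patient not having this symptom", sustained for 2 consecutive days. The activity items follow the same pattern. SAP 10.2.2 instead uses summed items 2-7 and 8-10, and lets the Q1 recovery date end them.

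**Evidence that Q1 and the items disagree.** SAP 12 records that "several patients still reported having symptoms while they reported they did not feel sick anymore at the question 1".

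**The concern.** The rule that ends measurement and the endpoints that use the measurements rest on different things. Q1 is one item of ten. With Q1 at 0, the other nine can still total up to 27. Protocol 7.1.3 speaks of all symptoms resolving but tests only Q1, so its wording does not agree with itself.

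The affected children are compliant. A child 'not sick' on D7 and D8 may correctly have no score for D9, D10 or D11, and V2 at D15-D18 falls outside the AUC window. The missing values come from the schedule, and they arise in the children whose parents report recovery first. If treatment affects when that happens, the amount of imputation can differ by arm.

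The SAP also reads the same residual answers in two ways. They count in the AUC and are carried to D11. In the durations they are discarded from the Q1 recovery date (10.2.2, section 12).

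**Working it through.** **1. Plan's own figure.** Inputs: d = 0.4, two-sided 5%, 80% power, 1:1 (Protocol 6.4 and 8.2). n per arm = 2(1.960 + 0.842)² / 0.4² = 98.1, so 99. The t-test version gives 99.08, so 100. Power at 100 per arm is 0.807 (normal) or 0.804 (t). The stated 100 per arm reproduces, and the point does not depend on it.

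**2. AUC weights.** With daily spacing, the trapezoidal rule from D1 to D11 gives weight 0.5 to D1 and D11 and weight 1 to D2-D10. The total is 10, so the scale runs from 0 to 30 × 10 = 300.

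| Last form | Unobserved days | Carried weight |
|---|---|---|
| D8 | D9, D10, D11 | 1 + 1 + 0.5 = 2.5 (25%) |
| D9 | D10, D11 | 1 + 0.5 = 1.5 (15%) |
| D10 | D11 | 0.5 (5%) |

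**3. Residual score r at the stop.** Setting D11 to the last value (SAP 6.4.7) makes the trapezoid across the gap flat, so it agrees with LOCF under Protocol 8.9.

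| Last form | Carried tail | Linear fall to 0 at D11 | 0 from next day | Overstatement |
|---|---|---|---|---|
| D8 | 3r | 1.5r | 0.5r | 1.5r to 2.5r |
| D9 | 2r | 1.0r | 0.5r | 1.0r to 1.5r |
| D10 | 1r | 0.5r | 0.5r | 0.5r |

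For a D8 stop, r = 2 gives 3 to 5 points and r = 4 gives 6 to 10 points. If r = 0 and stays 0, the error is 0. If the residual score really stays at r to D11, carrying it forward is exact.

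**4. Opposite direction.** Take a child who scores 0 on D8, stops, and would have scored 0, 5, 5 on D9-D11. The true tail is 0 + 2.5 + 5 = 7.5 and the carried tail is 0. The AUC is understated by 7.5.

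**5. From child to arm.** If affected children have the same mean error m in both arms, the shift in the mean difference is m × (share affected in device arm − share affected in placebo arm). The documents give neither quantity. As an assumption, take m = 1.5 to 10 points (r = 1 to 4 at D8) and an imbalance of 5 to 20 percentage points in either direction. The shift is then 1.5 × 0.05 = 0.075 to 10 × 0.20 = 2.0 points, of either sign. No SD of the AUC is given, so this cannot be set against d = 0.4.

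**6. Residual answers in the two analyses.** For a child 'not sick' on D7 and D8 with residual items and no later positive Q1, the recovery date is D7. The symptom duration ends no later than D6. The AUC counts the D7 and D8 items and repeats the D8 score to D11.

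**The case against.** A good deal can be said for the plan.

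- **The imputation was foreseen.** Protocol 8.9 names children who stop before D11, refers to 7.4 and specifies LOCF. This is a disclosed choice. That stands, but disclosure does not make a carried score correct when the items are not 0.
- **Most early stoppers may be symptom-free.** For them the carried value is 0 and nothing is lost unless they relapse. This stands. The documents show only that discordant children exist.
- **Durations are descriptive.** SAP 6.3.1 limits conclusions to the primary criterion, and SAP 12 discloses the Q1 rule. A severity sum and an end-of-illness date may also reasonably use different definitions. This lowers the weight of the duration part.
- **A relapse is not wholly invisible.** Events and medications are recorded to D15/D18, V2 includes an examination, and the SAP lists symptoms at end of study. A relapse is lost to the ARSSQ score, not necessarily to the trial.

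Two stronger readings are tempting. A reader might infer that the rule inflates the device arm's AUC and pulls the difference toward zero. That needs residual scores that are still falling and more such children in the device arm. The documents show neither, and an unseen relapse reverses the sign. A reader might also take the share imputed as 30%, because D8-D11 covers 3 of 10 intervals. But D8 is observed, so the imputed weight is 25%.

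**Conclusion.** The mismatch between schedule and endpoint is established from the text: collection can end at D8 on Q1 alone, while the primary AUC needs ten items to D11. The carried share is 25%, 15% or 5% for a stop at D8, D9 or D10. For an affected child who stops at D8 the overstatement is 1.5r to 2.5r, on the assumption that symptoms clear between D9 and D11. It is nil if all items are and remain 0, and the error is negative after an unrecorded relapse.

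The between-arm effect is not established in size or direction. It depends on an imbalance that the documents do not report; SAP 12 says only that several patients were discordant. The sample size is not in error. The change should be made because it removes avoidable imputation from the primary endpoint at little cost, not because a bias has been demonstrated.

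**What to change.** **Protocol and SAP text.** In the synopsis, 7.1.1, 7.1.3, 7.4.1 and the flow-chart footnotes of both documents, require the ARSSQ daily from D2 to D11 in every child, whatever Q1 says. After D11, continue until all ten items are 0 for 2 consecutive days, or V2. This changes only data collection and leaves the rule for stopping the device untouched. The weight imputed because of the stopping rule falls to 0.

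**Cost.** At most three more short forms by D11 for a recovered child, and more only while symptoms persist. There is no added visit. Protocol 7.4.1 already provides that "Parents/legal guardians will continue to complete the paper diary daily" up to D15/D18, for events and medications.

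**If the diaries are already collected.** This is likely, since the final SAP is dated August 2023 and section 12 describes answers already given. Report by arm how many children stopped under the Q1 rule with a non-zero score. Add to SAP 10.1 sensitivity AUCs for these stops:

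1. last score carried forward (current rule);
2. linear decline to 0 by D11;
3. 0 from the day after the stop;
4. residual items set to 0 from the Q1 recovery date, to match the duration rule;
5. a relapse scenario, applied also to children who stopped at 0.

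Option 3 alone would not be enough. It is the most favourable course after the stop: for a D8 stop it gives 0.5r, whereas a linear fall to 0 by D10 (r, r/2, 0, 0) gives r. It also leaves the D7-D8 residual items in the AUC although the duration rule drops them. The cost is programming and a few table rows.
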